1.0 Background & Rationale

Antibody-mediated rejection (ABMR) is a unique, significant and often severe form of allograft rejection. ABMR is characterized by several pathologic variants that are often resistant to treatment with standard immunosuppressive medications. Significant advances have occurred in our ability to predict patients at risk for and to diagnose ABMR ^{1,2}. The pathophysiology of ABMR suggests a prime role for antibodies, B-cells and plasma cells. As a result, IVIG, rituximab, and/or plasmapheresis (PLEX) have been leveraged for the treatment of acute ABMR³⁻⁷. Despite the success of these therapies, post-transplant ABMR, chronic active ABMR (cABMR), and transplant glomerulopathy (TG) remain significant problems that are often unresponsive to current therapies⁴. Data from the Deterioration in Kidney Allograft Function (DeKAF) study show that most graft losses in the current era of immunosuppression have evidence of cABMR with positive C4d staining^{2,8}. It is estimated that 5,000 renal allografts are lost each year in the US, primarily from cABMR and TG⁹. The current treatment paradigms rely on reduction of antibody levels to prevent ABMR. This raises the importance of maintaining immunosuppression and investigating novel methods to prevent and treat ABMR/cABMR that directly address the reduction of donor specific antibodies (DSAs) and antibody producing cells.

ABMR is frequently seen in patients receiving inadequate immunosuppression or who are noncompliant with anti-rejection medications and those who receive human leukocyte antigen (HLA)-incompatible transplants. In addition, TG is a known consequence of persistent DSA positivity which rapidly dissipates allograft function, resulting in graft failure and return to dialysis with attendant emotional consequences for the patients and financial consequences for the health care system ¹⁰⁻¹⁴. No current therapy is FDA approved and patients are often treated with combination therapies that make analysis of efficacy difficult. Thus, there is a large unmet clinical need. To this end, it is imperative that novel therapies to prevent immunologic injury to the microcirculation be developed and studied in patients with cABMR and TG.

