3.0 Primary Objectives

This study will be an open label design to assess the safety and efficacy of clazakizumab 25 mg SC given every 4 weeks (30 days) for a total of 6 doses in eliminating DSAs and stabilizing clinical features of cABMR in patients who have biopsy proven severe cABMR +TG. If improvements are seen in pathologic features of antibody mediated rejection from this biopsy compared to index biopsy, we will offer patients the opportunity to continue clazakizumab administrations monthly for an additional 6 months. A one year biopsy will then be performed at the end of the study. Safety determinations will be aimed at assessments of any side effects associated with clazakizumab administration and risk for infectious complications associated with clazakizumab therapy. Limited efficacy determinations will include assessment

of composite surrogate end points including patient and graft survival, stabilization of the clinical features of cABMR (eGFR, SCr) after clazakizumab treatment, and safety throughout study duration.

Long term primary objectives include:

- 1. assess the safety and efficacy of clazakizumab 12.5 mg or 25 mg SC given every 4-8 weeks in eliminating DSAs and stabilizing clinical features of cABMR in patients who have biopsy proven severe cABMR +TG
- 2. assess composite surrogate end points including patient and graft survival, stabilization of the clinical features of cABMR (eGFR, SCr) after clazakizumab treatment, and safety throughout study duration

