Background: This is a single center, Phase I/II, open label single-arm exploratory study. The trial will primarily examine the safety and tolerability of clazakizumab given after the diagnosis of cABMR in 10 subjects (15-75yrs) who exhibit DSAs to their donor. Patients entered will also have been diagnosed with cABMR + TG post-transplant based on Banff 2015 criteria. Patients are required to have a eGFR \geq 30 mL/min/1.73m² as calculated by the MDRD equation (Schwartz equation will be used to estimate CrCl for patients under 18 years of age) at entry. All patients will be recruited from the renal transplant program at Cedars-Sinai Medical Center. Once cABMR is diagnosed, donor-specific anti-HLA antibodies will be assessed (DSA) which are associated with cABMR and/or graft loss. DSA will be detected using solid phase assay systems currently utilized at the Cedars-Sinai Medical Center HLA Laboratory ([name] Director, [contact]. These anti-HLA antibodies may result naturally or from previous pregnancy, transfusions, or prior transplants. Patients treated with clazakizumab for cABMR will have labs for DSAs, and other monitoring labs as well as immunologic studies as outlined (See Study Protocol in Appendix A). In addition to the standard post-transplant immunosuppressive protocol, patients with cABMR will receive clazakizumab 25mg SC given every 4 weeks (30 days) for a total of 6 doses. If no safety/tolerability/efficacy issues are observed after the initial dose, patients will continue the protocol as outlined (see Appendix A). A protocol biopsy will be performed after the 6th and after the 12th doses of clazakizumab (as mentioned before) to assess the allograft for evidence of cABMR/ABMR, including C4d staining and TG using Banff 2015 criteria¹⁴. Banff scoring will be compared between the index and protocol biopsy after cessation of therapy. Patients who have evidence of persistent allograft dysfunction may have non-protocol biopsies for cause. After completion of the clazakizumab therapy, patients will be followed up to assess allograft function and ABMR episodes as well as DSAs. The protocol is summarized in figure 14 below. Monitoring of Treg, Thir, Tfh and plasmablast as well as IL-6

and CRP level will be performed in the Transplant Immunology Lab at Cedars-Sinai Medical Center at select time points ([name] Director, [contact]).

[figure not shown]

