Figure 14: This figure shows the protocol designed to investigate the safety and efficacy of clazakizumab in treating cABMR + TG. The study is open label, single center one-arm study that will enter patients diagnosed with cABMR + TG by renal biopsy and who have eGFR of > 30cc/min at time of diagnosis. Entered patients will receive clazakizumab 25mg every 4 weeks (30 days) for a total of 6 doses. If patients show improvement (ie: eGFR/DSA/biopsy/PI confirmation) they will continue monthly clazakizumab for an additional 6 months and will have a second biopsy at 12 month protocol. Immunologic and viral monitoring labs will be performed as indicated. For those continuing in the long term extension, the day 365 visit will be followed by visits every 4-8 weeks.

The subjects will be followed to determine if the use of clazakizumab for treatment of cABMR in this high-risk transplant population is safe and without infectious risks. In addition, we will determine the effects of clazakizumab treatment on renal biopsy assessments performed at 6 months. Assessments of renal function, donor specific antibody, and Banff 2015 biopsy scores will be evaluated at that time. If improvement or stabilization observed, clazakizumab will be resumed monthly x 6 doses (starting day 180 to day 330) and last study visit will be day 365 with biopsy for those who are not continuing to the long term extension. For those continuing in the long term extension, the day 365 visit will be followed by visits every 4- 8 weeks, per the schedule in Appendix E. We will assess the transplanted patients to determine the number who sustain a viable and functioning kidney allograft as well. In the event a patient does not show improvement after receiving 6 doses of clazakizumab, no further treatment will be given and the patient will return at Day 365 for a final study visit. All subjects will be evaluated on an intent-to-treat basis. The subject accrual rate will be limited to 2 patients for the initial dosing appointment. Once the first 2 patients have received their first injection, 2-4 patients may be screened per month until all 10 patients are enrolled. Repeat laboratories will be performed at the completion of clazakizumab therapy to determine effect on levels and correlation with any potential events. A detailed analysis of the study is discussed below.

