4.1 Study Analysis

This single-center, single-arm, Phase I/II, trial is designed to examine the safety, tolerability and limited efficacy of human clazakizumab (25mg SC Q4W) given as per protocol (Appendix A) in 10 subjects who are DSA + and have biopsy proven cABMR + TG. Patients considered for this study may have been treated with high-dose IVIG + rituximab and/or plasmapheresis^{3,6,7} In addition, some patients with early, severe ABMR may have been treated with Eculizumab⁴².

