4.6 Infection Prophylaxis Protocols and Viral Monitoring Post-Transplant

All study patients, regardless of their cytomegalovirus (CMV) status, receive IV ganciclovir while inpatients and valganciclovir as outpatients for 6 months post kidney transplant, with dose adjustments for renal function. Fungal prophylaxis was accomplished with fluconazole 100 mg daily for 1 month post transplant. Pneumocystis jirovecii pneumonia and bacterial prophylaxis is accomplished with trimethoprim 80 mg and sulfamethoxazole 400 mg daily for 12 months post transplant. No additional prophylaxis will be needed for patients who are enrolled in this trial more than one year from transplant.

Viral polymerase chain reaction assays for CMV, Epstein Barr virus, Parvovirus B-19, Polyoma virus BK and JC will be performed on study patients monthly for 6 months post-transplantation. Methodologies used for monitoring viral replication have been described previously ²⁵.

5 Dosing of Clazakizumab

For antibody mediated rejection: Clazakizumab will be administered at a dose of 25mg/SC every 4 weeks post pulse methylprednisolone, plasmapheresis, and high dose IVIG. If the patient proceeds to the LTE, they will receive clazakizumab 12.5 mg or 25 mg SC Q4W or Q8W.

Product Description, Storage and Administration Instructions

Clazakizumab will be provided by CSL Behring LLC.

Generic name: Clazakizumab

Active ingredient: Genetically engineered humanized anti-IL-6 mAb

Strength: 12.5 mg/mL (once the 25 mg/mL concentration was no longer available)

Excipients: L-histidine, L-histidine monohydrochloride, sorbitol, polysorbate-80, and water for injection

Appearance: Clear to slightly opaque, colorless to dark yellow-colored solution

Dosage form: Single-dose vials (25 mg/mL or 12.5 mg/mL) for injection.

Manufacturer: Ajinomoto Althea, San Diego CA

Patheon Manufacturing Services LLC, Greenville, NC

Clazakizumab vials should be stored at ≤-20°C (-4°F) with protection from light.

The drug product will be administered undiluted at a concentration of 12.5 mg/mL.

Prepared syringes may be stored for up to 24 hours in a refrigerator, 2°-8°C (36°-46°F), and up to 4 hours of the 24 hours may be at room temperature, 15°-25°C (59°-77°F). The prepared syringes should be protected from light.

Prior to administration, clazakizumab should reach room temperature by storing unrefrigerated for 30 to 60 minutes before use.

IP requests should be sent to: [contact]

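### Section 5 makes steroid pulse, plasmapheresis and IVIG an unconditional lead-in to clazakizumab, against Section 4.1 and Appendix A, and no DSA or eGFR is marked at Day 0 to separate their effect

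*Protocol*

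**What the plan says.** The dosing rule in the protocol, Section 5 (Dosing of Clazakizumab), reads: "Clazakizumab will be administered at a dose of 25mg/SC every 4 weeks post pulse methylprednisolone, plasmapheresis, and high dose IVIG". It gives no dose, number of sessions or interval for the three preceding therapies and does not say that they are optional.

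Section 4.1 (Study Analysis) treats earlier therapy as a possibility: "Patients considered for this study may have been treated with high-dose IVIG + rituximab and/or plasmapheresis". It adds that "some patients with early, severe ABMR may have been treated with Eculizumab". Pulse methylprednisolone is not on that list.

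Three other places give the regimen and do not mention a lead-in. Section 3.0 sets out to assess "efficacy of clazakizumab 25 mg SC given every 4 weeks (30 days) for a total of 6 doses in eliminating DSAs". Section 4 (Study Design & Methods) says "In addition to the standard post-transplant immunosuppressive protocol, patients with cABMR will receive clazakizumab 25mg SC given every 4 weeks". The Figure 14 legend says "Entered patients will receive clazakizumab 25mg every 4 weeks (30 days) for a total of 6 doses".

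Appendix A has no row or visit for steroid pulses, plasmapheresis or IVIG; treatment starts with injection 1 at Day 0. DSA and estimated GFR are marked at Screening (-15 days), blank at Day 0, and marked again at Day 30 ± 7 days.

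**The concern.** The study has one arm, 10 patients and no concurrent control, so the effect on DSA and renal function is read as change within patients. Section 7 disclaims power for efficacy, but it names the effect on circulating DSA, together with tolerability, as most important. Improvement in GFR and DSA also feeds the Day 180 decision on six further doses, alongside the biopsy and the investigator's confirmation.

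The protocol does not regard the Section 5 therapies as inert. Section 1.0 says "The current treatment paradigms rely on reduction of antibody levels to prevent ABMR" and names IVIG and plasmapheresis among the treatments used for acute ABMR. If every patient received them before dose 1, the before-after change would describe a package of treatments. The safety reading would be affected too, because Section 3.0 aims to assess infectious complications associated with clazakizumab, and a lead-in of further immune-directed therapy blurs that attribution.

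**Working it through.** The plan gives no figure to reproduce here. The check sets the texts side by side and reads the columns of Appendix A.

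**Status of the preceding therapy, place by place**

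- Section 5: required as worded; pulse methylprednisolone, plasmapheresis and high-dose IVIG; no interval.
- Section 4.1: possible, not required; high-dose IVIG with rituximab and/or plasmapheresis, and eculizumab in some; no pulse steroid.
- Appendix A: no lead-in scheduled; the first treatment is injection 1 at Day 0.
- Sections 3.0 and 4 and the Figure 14 legend: silent. Section 4 adds only the standard immunosuppressive protocol. The figure itself is not reproduced in the text available.
- Section 4.3: pulse steroid, IVIG and plasma exchange appear, with doses and schedules, but only as treatment for rejection during the study.

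Section 5 therefore conflicts with Section 4.1 on both status and content, and with Appendix A on the schedule. The silent places do not contradict it, but none of them supports it.

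**Eligibility.** Sections 3.2 and 3.3 set no washout for IVIG, plasmapheresis or steroids. The only washout for a treatment other than vaccines or antibiotics is 4 weeks for investigational agents. The criteria therefore do not fix when such therapy ended.

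**Pre-dose measurements in Appendix A**

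- DSA: Screening marked, Day 0 blank, Day 30 marked.
- Estimated GFR: Screening marked, Day 0 blank, Day 30 marked.
- Safety laboratory tests, including the chemistry panel: Screening marked, Day 0 blank, Day 30 marked.
- IgG, CRP, the anti-drug antibody, IL-6 and PK samples, and the cell assays: Day 0 marked.

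The last group shows that the Day 0 column was not lost and that blood is already drawn that day.

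**Gap.** If the -15 days in the Screening header is read as a window, the last scheduled DSA and eGFR fall 0 to 15 days before dose 1. For any one patient:

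observed change = (change from Screening to dose 1) + (change after dose 1).

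Without a Day 0 value, the two terms cannot be separated. If therapy falls in the gap, its effect up to dose 1 sits in the first term and is counted in the total. If therapy ended and its effect settled before Screening, the first term contains none of it.

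The protocol does not state when the therapy is given and sets no DSA threshold for improvement. Neither a size nor a direction of error can be calculated.

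**The case against.** The strongest reply is that Section 5 is loose or leftover wording. Its sentence is introduced as applying to antibody-mediated rejection, gives no details for the three therapies, and could simply describe patients who had been treated earlier, as Section 4.1 does. Where the protocol really prescribes these treatments, in Section 4.3, it gives doses. This is a plausible account of intent. But the sentence stands in the dosing section, directly before the current long-term extension doses, and the label barely narrows it: the definition of ABMR in Section 4.2 itself includes biopsy evidence of cABMR and TG. A site reading it has no basis for treating it as optional.

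A second reply is that the baseline problem needs timing the protocol does not give. This stands. The past tense of Section 4.1 points to therapy before Screening, in which case a settled effect is already in the Screening value. The baseline point is therefore conditional.

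Third, the notes to Appendix A are not visible in the text available, so a note on sample timing cannot be excluded. The schedule point rests on the marked cells. The conflict between Sections 5 and 4.1 does not depend on those notes.

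Fourth, DSA change alone does not decide continuation: biopsy and investigator confirmation also count, and stabilization qualifies as well ("If improvement or stabilization observed, clazakizumab will be resumed monthly x 6 doses"). This is also correct and limits what is at stake at Day 180.

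**Conclusion.** The inconsistency is real and should be fixed. Section 5 states as a rule what Section 4.1 only permits and Appendix A does not schedule. Followed literally, it would give all 10 patients co-therapy aimed at the same antibody, and the DSA, eGFR and infection results could not be attributed to clazakizumab alone. No formal test is affected, since the study is exploratory and not powered for efficacy.

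The schedule adds a conditional weakness: there is one pre-dose DSA and eGFR, 0 to 15 days before dose 1, and none marked at Day 0. This assumes that the Screening header denotes a window and that no unseen note to Appendix A changes the sampling.

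A reader might infer more than this. One inference is that the DSA result is biased in favour of clazakizumab, or that the length of the gap measures the bias. The documents support neither: nothing places the therapy between Screening and dose 1, and elapsed time is not DSA or eGFR error. The improved graft survival reported in the Figure 1 legend concerns a different regimen and a different outcome, so it does not size the problem. Another inference is that DSA would rebound after plasmapheresis and hide a benefit; the protocol gives no data on that. Finally, allowing prior therapy, as Section 4.1 openly does, is a legitimate choice and is not at fault.

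**What to change.** 1. Reword the Section 5 sentence to agree with Section 4.1: earlier rejection therapy is permitted, not required. If the lead-in is intended, state it and its interval in Sections 3.0, 4, 4.1 and 5, the Figure 14 legend and Appendix A, and word the conclusion as clazakizumab following those therapies.

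2. Add a pre-dose DSA and a serum creatinine (for eGFR) to the Day 0 draw already scheduled for IgG, CRP and PK. Report change from both the Screening and the Day 0 values.

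The cost is a small text amendment and, with 10 patients, about ten DSA assays and ten creatinines on an existing draw. Two baselines must be shown, and the reported DSA reduction may turn out smaller. The Day 0 sample separates only what happened before dose 1. Carry-over from earlier therapy that continues after Day 0 is not removed and remains a limit of a single-arm design.

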5.1 Storage and Handling

Clazakizumab will not be used after the expiry date (EXP) shown on the kit or vial.

5.1.1 Clazakizumab Overdose

There are no specific antidotes or measures to take in the event of an overdose of clazakizumab injection. Subjects should be treated with the appropriate supportive care.

5.2 Dose Modification/Toxicity Management

A number of measures will be taken to ensure the safety of patients participating in this study. These measures will be addressed through exclusion criteria (see Section 4.2) and routine monitoring as follows:

Patients enrolled in this study will be evaluated clinically and with standard laboratory tests before and during their participation in this study. Safety evaluations will consist of medical interviews, recording of adverse events, physical examinations, blood pressure, and laboratory measurements. Subjects will be evaluated for adverse events (all grades), serious adverse events, and adverse events requiring study drug interruption or discontinuation at each study visit for the duration of their participation in the study.

5.3 Adverse Drug Reactions

Opportunistic Infections and Serious Infections

Physicians should exercise caution when considering the use of clazakizumab in patients with a history of recurring infection or with underlying conditions (eg, diabetes) which may predispose patients to infections. Clazakizumab should not be administered in patients with active infection. The effects of clazakizumab on CRP, neutrophils, and the signs and symptoms of infection should be considered when evaluating a patient for a potential infection.

Vigilance for timely detection of serious infection is recommended for patients receiving biologic agents for treatment of moderate to severe RA as signs and symptoms of acute inflammation may be lessened due to suppression of the acute phase reaction. Patients must be instructed to contact their physician immediately when any symptoms suggesting infection appear, in order to assure rapid evaluation and appropriate treatment.

If a patient develops a serious infection, administration of clazakizumab is to be interrupted until the infection is controlled. The clinician should consider the benefit-risk before resuming treatment with clazakizumab.

Gastrointestinal Perforations

Timely diagnosis and appropriate treatment may reduce the potential for complications of diverticulitis and thus reduce the risk of GI perforations. Therefore, patients should be made aware of the symptomatology potentially indicative of diverticular disease, and they should be instructed to alert their healthcare provider as soon as possible if these symptoms arise. In patients with a history of symptomatic diverticulosis, diverticulitis or chronic ulcerative lower GI disease such as Crohn's disease, ulcerative colitis or other chronic lower GI conditions that might predispose to perforations, the clinician should consider the benefit-risk before using clazakizumab. Discontinuation of clazakizumab is recommended for patients who develop GI perforations.

Demyelinating Disorders

The impact of treatment with clazakizumab on demyelinating disorders is not known; events were rarely reported. Patients should be closely monitored for signs and symptoms potentially indicative of central demyelinating disorders. Physicians should exercise caution in considering the use of clazkizumab in patients with pre-existing or recent onset demyelinating disorders. Treatment with clazakizumab should be interrupted during assessment of a potential demyelination event and only resumed if the benefit of continuing study drug is favorable.

Hematologic Abnormalities and Bleeding Events

Decreases in neutrophil and platelet counts have been observed following treatment with clazakizumab in combination with MTX. In addition, there may be an increased risk of neutropenia in patients who have previously been treated with a TNF antagonist.

For patients with concomitant medications associated with hematologic toxicity, the reduction or interruption of the suspected medication is recommended prior to modifying clazakizumab.

Table 2: Neutropenia Risk Mitigation

ANC (cells/mm³)	Action
> 1000	Maintain dose.
500 – 1000	Interrupt clazakizumab dosing.
	When ANC increases to > 1000, resume clazakizumab 25mg SQ monthly
< 500	Discontinue clazakizumab.

Table 3: Thrombocytopenia Risk Mitigation

Platelet count (cells/mm³)	Action
> 100,000	Maintain dose.
50,000 - 100,000	Interrupt clazakizumab dosing.
	When platelet count increases to > 100,000, resume
	Clazakizumab at 25mg SQ monthly
< 50,000	Discontinue clazakizumab.

Elevated Liver Enzymes and Hepatic Events

Elevations in ALT and AST have been observed during treatment with the study medications

Table 4:

Lab Value	Action
> 1 to 3x ULN	Dose modify concomitant transplant immunosuppressive drugs if appropriate For persistent increases in this range, interrupt clazakizumab until ALT/AST have normalized

	Restart with 25mg SQ monthly as clinically appropriate				
> 3 to 5x ULN	Interrupt clazakizumab dosing until < 3x ULN and follow				
(confirmed by repeat	recommendations above for >1 to 3x ULN				
testing)	For persistent increases > 3x ULN, discontinue Clazakizumab				
	Discontinue clazakizumab if total bilirubin >2 x ULN				
> 5x ULN	Discontinue clazakizumab				

Cardiovascular Events and Elevated Lipids

Patients with RA have an increased risk for cardiovascular disorders, therefore, risk factors for cardiovascular disease (eg, hypertension, hyperlipidemia) should be managed as part of their standard of care. See section on Drug Interactions.

For patients with LDL cholesterol ≥160 mg/dL, it is strongly recommended that investigators advise therapeutic lifestyle changes that may include initiation lipid-lowering agents. Lipid-lowering agents should also be considered for patients with lower LDL cholesterol levels as part of their therapeutic lifestyle changes depending on their overall risk as defined in NCEP ATP III or other national guidelines.

Malignancies

The impact of immunosuppression on the development of malignancies is not known, however an increased rate of some malignancies, notably lymphoma, has been observed in RA patients. Although no imbalance of malignancies was observed in clinical trials of clazakizumab, malignancies have been identified as a concern for other biologics. It is recognized that identification of such events in clazakizumab-treated patients may require a longer period of surveillance. Clazakizumab should be discontinued in patients with malignancies (with the exception of local basal or squamous cell carcinoma of the skin that is completely excised with free margins).

Hypersensitivity or Anaphylaxis:

An infusion/dose reaction is defined as an adverse event occurring during and within 24 hours after the infusion or subcutaneous injection of clazakizumab. This may include hypersensitivity reactions or anaphylactic reactions.

Signs of a possible hypersensitivity reaction include but are not limited to:

- · fever, chills, pruritus, urticaria, angioedema, and skin rash.
- cardiopulmonary reactions, including chest pain, dyspnea, hypotension or hypertension.

Healthcare professionals administering clazakizumab should be trained in the appropriate administrative procedures, be able to recognize the symptoms associated with potential anaphylactic or hypersensitivity reactions, and have the appropriate medication available for immediate use in case of anaphylaxis or hypersensitivity reaction during or after

administration of clazakizumab. Healthcare professionals should also instruct patients to seek medical attention if they experience symptoms of a hypersensitivity reaction outside of the clinic.

If a patient has symptoms of anaphylaxis or serious hypersensitivity, or requires an interruption of the study drug because of symptoms of anaphylaxis or hypersensitivity, administration of clazakizumab must be discontinued permanently. The patient should be treated according to the standard of care for management of the hypersensitivity reaction. A blood sample for the presence of anti-clazakizumab antibodies should be obtained.

Clazakizumab should not be administered to subjects who have had any previous allergic reactions to monoclonal antibodies. To date, no infusion reactions have been associated with clazakizumab administered by IV infusion. Injection site reactions have been reported with SC administration. Reactions have been mild or moderate and have resolved without treatment. Both allergic reactions and injection site reactions should be treated with standard of care. Subjects who have developed significant allergic reaction to study drugs should not be re-challenged.

Viral Reactivation

Though rarely reported within the clazakizumab program due to exclusion criteria at study entry, reactivation of viral and other serious infections (e.g. EBV or TB) has been observed with biologic therapies.

Drug Interaction

The formation of CYP450 enzymes may be suppressed by increased levels of cytokines (eg, IL-6) during chronic inflammation. Therefore, it is expected that for molecules that antagonize cytokine activity, such as clazakizumab, the formation of CYP450 enzymes could be normalized. When starting or stopping therapy with clazakizumab, patients taking medications which are individually dose-adjusted and metabolized via CYP450, 3A4, 1A2, or 2C9 (e.g. atorvastatin, calcium channel blockers, theophylline, warfarin, phenytoin, cyclosporine, or benzodiazepines) should be monitored as doses may need to be adjusted to maintain their therapeutic effect. Given its long elimination half-life (t1/2), the effect of clazakizumab on CYP450 enzyme activity may persist for several weeks after stopping therapy.

Pregnancies and Women of Child Bearing Potential

A total of 9 pregnancies were reported from the clazakizumab completed clinical studies. Eight were exposed to clazakizumab, and 1 to placebo. Of the 8 pregnancies that were exposed to clazakizumab, 5 were maternal exposure and 3 were paternal exposure. Eight pregnancies occurred in subjects enrolled in rheumatoid or psoriatic arthritis studies, who received concomitant low-dose MTX which is a known human teratogen with an increased risk of spontaneous abortions, intrauterine growth restriction, and congenital malformations in case of exposure during pregnancy. (https://www.medicines.org.uk/emc/product/511/smpc)

The outcomes after maternal exposure were as follows:

1 normal newborn, 2 spontaneous abortions, 1 missed abortion, and 1 intrauterine growth retardation.

The outcomes after the paternal exposures were as follows:

1 spontaneous abortion, 1 unknown outcome, and 1 baby born with Mosaic Down's syndrome.

The investigator considered that 1 spontaneous abortion (Study IM133001) and the missed abortion (Study IM133004) after maternal exposure were related to clazakizumab and MTX treatment. All other pregnancy outcomes were considered as unrelated to clazakizumab.

In the US general population, the estimated background risk of major birth defects is 2% to 4% and the rate of miscarriage in clinically recognized pregnancies is 15% to 20% (https://www.fda.gov/media/90160/download).

Due to the confounding effect of MTX treatment and the general background risk of major birth defects and miscarriage in clinically recognized pregnancies, the role of clazakizumab is unknown.

Insufficient data is available from pregnancy exposure in clinical studies to date to inform on the potential harm of clazakizumab use during pregnancy. All subjects of child bearing potential being treated with clazakizumab (and their partners) must be informed of this risk, and use highly effective birth control. Administration of clazakizumab may decrease the efficacy of hormonal oral contraceptives.

Under no circumstances shall clazakizumab injection be administered to women known to be pregnant or lactating.

6 Therapy Stopping Points

As indicated previously, the study will be halted and re-evaluated by the Data and Safety Monitoring Board (DSMB) if any patient in the study group develops SAEs or evidence of severe infusion related or infectious complications. In addition the study will be reevaluated if a patient develops worsening ABMR while in treatment, possibly indicating lack of efficacy of clazakizumab (see appendix C).

7 Statistical Analysis

Due to the exploratory nature of this study that involves safety endpoints only and the small sample size that is not powered for efficacy end points, our primary objective will be to assess safety end points and limited efficacy. Most important will be tolerability in the ESRD population and determination of the effects of clazakizumab treatment on circulating DSAs as well as the ability to improve outcomes of patients with cABMR and TG. We will however plan to assess biopsies 6M post-transplantation in patients desensitized with clazakizumab treatment to determine if there are durable effects in prevention of ABMR both acute and chronic.

8 References

- 1. Colvin RB. Antibody-mediated renal allograft rejection: diagnosis and pathogenesis. J Am Soc Nephrol 2007;18:1046-56.
- 8. Sellarés J, de Freitas DG, Mengel M, et al. Understanding the causes of kidney transplant failure: the dominant role of antibody-mediated rejection and nonadherence. Am J Transplant 2012;12:388-99.
